3.4.4 Guidelines for Visual Changes

Trametinib is known to be associated with visual adverse events. An ophthalmologist should be consulted if changes in vision develop. However, if the visual changes are clearly unrelated to study treatment (e.g., allergic conjunctivitis), then monitor closely as it may be reasonable to defer ophthalmic examination. Special attention should be given to retinal findings (e.g., retinal pigment epithelial detachment (RPED) or retinovascular abnormalities (i.e., branch or central retinal vein occlusions [RVO]).

The ophthalmology exam will include best corrected visual acuity, visual field examination, tonometry, slit lamp biomicroscopic examination, and indirect fundoscopy. Optical coherence tomography is recommended at scheduled visits and if retinal abnormalities are suspected. Other types of ancillary testing including visual field examination, fundus photography, and fluorescein angiography may also be indicated as determined by clinical exam.

Guidelines regarding event management and dose reduction for visual changes considered to be related to study treatment are provided in Tables 4 and 5.

Table 4 Management and Dose Modification Guidelines for Visual Changes and/or Ophthalmic Examination Findings

CTCAE Grade ^{a,c}	Adverse Event Management	Action and Dose Modification
Grade 1 ^b	
 Consult ophthalmologist within 7 days of onset 	
 If dilated fundus examination cannot be performed within 7 days of onset, interrupt trametinib until RPED and RVO can be excluded by retina specialist/ophthalmologist. If RPED and RVO excluded, continue/or restart trametinib at same dose level If RPED suspected or diagnosed: see RPED dose modification table below (following this table); report as SAE. If RVO diagnosed: Permanently discontinue trametinib and report as SAE.
Grade 2 and Grade 3	
 Consult ophthalmologist immediately 	
 Hold trametinib If RPED and RVO excluded, restart trametinib at same dose level after visual AE is ≤ grade 1. If no recovery within 4 weeks, discontinue trametinib If RPED diagnosed, see RPED dose modification table below; report as SAE. If RVO diagnosed: Permanently discontinue trametinib and report as SAE
Grade 4	
 Consult ophthalmologist immediately Report as SAE 	
 Hold trametinib If RPED and RVO excluded, may restart trametinib at same or reduced dose after discussion with the subprotocol Study Chair. If RVO or RPED diagnosed, permanently discontinue trametinib

Rev. 8/15

Abbreviations: RPED = retinal pigment epithelial detachment; CTCAE = Common Terminology Criteria for Adverse Events;

RVO= retinal vein occlusion; SAE = serious adverse event

a. Refers to CTCAE Version 4.0 'Eye disorders – Other, specify'

b. If visual changes are clearly unrelated to study treatment (e.g., allergic conjunctivitis), monitor closely but ophthalmic examination is not required.

c. Refers to CTCAE Version 4.0 'Retinopathy'

Table 5 Recommended dose modifications for trametinib for retinal pigment epithelial detachments (RPED)^a

CTCAE Grade	Action and Dose Modification
Grade 1 RPED (Asymptomatic; clinical or diagnostic observations only)	
 Continue treatment with retinal evaluation monthly until resolution. If RPED worsens follow instructions below
Grade 2-3 RPED (Symptomatic with mild to moderate decrease in visual acuity; limiting instrumental ADL)	
 Interrupt trametinib Retinal evaluation monthly If improved to ≤ Grade 1, restart trametinib at lower dose (reduced by 0.5 mg) or discontinue in patients taking trametinib 1 mg daily If no recovery within 4 weeks, permanently discontinue trametinib

3.4.5 Pneumonitis Management Guidelines

Pneumonitis has been observed in subjects receiving trametinib. To reduce the risk of pneumonitis, subjects will be monitored closely for symptoms, evaluated with imaging and functional tests. Dose modification and supportive care guidelines for pneumonitis are described (see Table 6).

Rev. 8/15 **Table 6 Pneumonitis Guidelines for Trametinib**

CTCAE Grade	Adverse Event Management	Action and Dose Modification
Grade 1	
 CT scan (high-resolution with lung windows) recommended Clinical evaluation and laboratory work-up for infection Monitoring of oxygenation via pulse-oximetry recommended Consultation with pulmonologist recommended 	
 Continue trametinib at current dose
Grade 2	
 CT scan (high-resolution with lung windows) recommended Clinical evaluation and laboratory work-up for infection Consult pulmonologist Pulmonary function tests -if < normal, repeat every 8 weeks until ≥ normal Bronchoscopy with biopsy and/or BAL recommended Symptomatic therapy including corticosteroids if clinically indicated 	
 Interrupt trametinib until recovery to grade ≤ 1 Restart treatment with trametinib reduced by one dose level Escalation to previous dose level after 4 weeks and consultation with the subprotocol Study Chair possible If no recovery to grade ≤ 1 within 2 weeks, permanently discontinue trametinib
Grade 3	
 Same as Grade 2 	
 Interrupt trametinib until recovery to grade ≤1 After consultation with the subprotocol Study Chair, treatment with trametinib may be restarted reduced by one dose level If no recovery to grade ≤ 1 within 2 weeks, permanently discontinue trametinib
Grade 4	
 Same as grade 2 	
 Permanently discontinue trametinib

Abbreviations: BAL= bronchioalveolar lavage; CT = computed tomography; CTCAE = Common Terminology Criteria for Adverse Events

Rev. 12/16

3.5 **Dose Modifications for Trametinib and supportive care**

3.5.1 **Trametinib Dose Modification for Liver Chemistry Changes**

Table 7: Trametinib Dose Modification for Liver Function Test Abnormalities

Event	Treatment modifications and assessment/monitoring

ALT \geq 3x ULN but < 5x ULN and TB < 2x ULN, without symptoms considered related to liver injury or hypersensitivity and who can be monitored weekly for 4 weeks
	
 • May continue study drug. • Report as SAE if CTEP-AERS reporting criteria is met. • If liver chemistry stopping criteria are met any time, proceed as described below. 
MONITORING:
 
Repeat LFT (ALT, AST, ALK, bilirubin) until they return to normal/baseline or stabilise (LFT may be every 2 weeks after 4 weeks if ALT < 3x ULN and TB < 2 ULN). If baseline ALT and Tbili already meet these criteria, then monitoring is required only if ALT or TB rises after initiation of study therapy.


Criteria for discontinuing study drug: When any of the liver stopping criteria below is met, discontinue trametinib
 
 1. ALT \geq 3xULN and bilirubin \geq 2x ULN or > 35% direct bilirubin ^{1, 2} 2. ALT \geq 3xULN and INR >1.5, if INR measured² (INR threshold does not apply if subject is on anticoagulant) 3. ALT \geq 5x ULN 4. ALT \geq 3x ULN persists for \geq 4 weeks. However, if ALT was elevated 3-5x at baseline due to liver mets, then this criteria should not be used for treatment discontinuation UNLESS the ALT improves to <3x ULN and then subsequently rises. 5. ALT \geq 3x ULN and cannot be monitored weekly for 4 weeks. However, if ALT was elevated 3-5x at baseline due to liver mets, then this criteria should not be used for treatment discontinuation UNLESS the ALT improves to < 3x ULN and then subsequently rises. 6. ALT \geq 3x ULN associated with symptoms³ (new or worsening) believed to be related to liver injury or hypersensitivity 	
 • Immediately discontinue study treatment. • Do not restart/rechallenge unless approved by the subprotocol Study Chair. [• Report as SAE if: 1) CTEP-AERS reporting criteria are met, or 2) patients meet criteria 1-2. • Perform liver event ASSESSMENT AND WORKUP (see below). • Monitor the subject until liver chemistries resolve, stabilize, or return to baseline (see MONITORING below). 
• [
 
MONITORING:
 
In patients stopping for criteria 1-2 (with abnormal TB and INR, indicating potentially more significant liver toxicities):
 
 • Repeat liver chemistries (ALT, AST, ALK, bilirubin) and perform liver event follow-up assessments within 24 hours. • Monitor subjects twice weekly until LFT return to normal/baseline or stabilize. • A specialist or hepatology consultation is recommended. 
In patients stopping for criteria 2-6:
 
 • Repeat LFT and perform liver event follow up assessments within 24-72 hrs • Monitor subjects weekly until LFTs return to normal/baseline or stabilize. 
ASSESSMENT and WORKUP:
 
 • Viral hepatitis serology.⁴ • Serum CPK and LDH. • Fractionate bilirubin, if total bilirubin \geq 2x ULN. • CBC with differential to assess eosinophilia. • Record clinical symptoms of liver injury, or hypersensitivity on AE CRF. • Record concomitant medications (including acetaminophen, herbal remedies, other over the counter medications). • Record alcohol use. 
Additional work up for patient stopping for criteria 1-2 (with abnormal TB and INR, indicating potentially more significant liver toxicities):
 
 • Anti-nuclear antibody, anti-smooth muscle antibody, Type 1 anti-liver kidney microsomal antibodies, and quantitative total

Rev. 8/15

Rev. 12/16

Event	Treatment modifications and assessment/monitoring
	immunoglobulin G (IgG or gamma globulins). 
 • Serum acetaminophen adduct HPLC assay (in subjects with likely acetaminophen use in the preceding). • If there is underlying chronic hepatitis B (e.g. positive hepatitis B surface antigen): quantitative hepatitis B DNA and hepatitis delta antibody.⁵ • Liver imaging (ultrasound, MRI, CT) and /or liver biopsy.
Footnotes: 
 1. Serum bilirubin fractionation should be performed if testing is available. If serum bilirubin fractionation testing is unavailable, record presence of detectable urinary bilirubin on dipstick, which indicates direct bilirubin elevations and suggesting liver injury. 2. All events of ALT \geq 3xULN and bilirubin \geq 2xULN (> 35% direct bilirubin) or ALT \geq 3x ULN and INR > 1.5 (if INR measured) may indicate severe liver injury (possible "Hy's Law"). INR measurement is not required, and the threshold value stated will not apply to subjects receiving anticoagulants. 3. New or worsening symptoms believed to be related to liver injury (such as fatigue, nausea, vomiting, right upper quadrant pain or tenderness, or jaundice) or believed to be related to hypersensitivity (such as fever, rash or eosinophilia) 4. Includes: Hepatitis A IgM antibody; Hepatitis B surface antigen and Hepatitis B Core Antibody (IgM); Hepatitis C RNA; Cytomegalovirus IgM antibody; Epstein-Barr viral capsid antigen IgM antibody (or if unavailable, obtain heterophile antibody or monospot testing); Hepatitis E IgM antibody 5. If hepatitis delta antibody assay cannot be performed, it can be replaced with a PCR of hepatitis D RNA virus (where needed) (Le Gal et al., 2005). 	

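### Liver stopping criterion 1 and its own footnote relate the direct bilirubin fraction to total bilirubin differently, so the same laboratory values can meet or miss the criterion

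*Protocol*

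**What the plan says.** All of these lines are in the protocol, in Section 3.5.1, Table 7, unless stated otherwise.

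- **Criterion 1.** ALT at least 3×ULN and bilirubin at least "2x ULN or > 35% direct bilirubin". It carries footnotes 1 and 2.
- **Section 3.2.1, Liver Chemistry Changes.** The expedited-reporting trigger has the same ALT condition and the same unbracketed connector.
- **Footnote 2.** It names the events that may indicate severe liver injury (possible Hy's Law). The bilirubin part reads "2xULN (> 35% direct bilirubin) or ALT"; the last two words begin the separate INR alternative.
- **Footnote 1.** "Serum bilirubin fractionation should be performed if testing is available". No total-bilirubin threshold is given.
- **Assessment and work-up.** "Fractionate bilirubin, if total bilirubin" is at least 2×ULN.
- **Monitoring and additional work-up for criteria 1–2.** Both headings describe these patients as having abnormal total bilirubin and INR.
- **First row.** A patient with ALT at least "3x ULN but < 5x ULN and TB < 2x ULN, without symptoms considered related to liver injury or hypersensitivity", who can be monitored weekly, is given the action "May continue study drug". The row adds: "If liver chemistry stopping criteria are met any time, proceed as described below".

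**The concern.** Criterion 1 offers the direct fraction as an alternative to a raised total bilirubin. Footnote 2 attaches it to a total that is already raised. These are different logical conditions on the same three measurements.

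The consequences of meeting criterion 1 are substantial: immediate discontinuation, no restart without the subprotocol Study Chair's approval, an SAE report, repeat chemistries within 24 hours, twice-weekly monitoring and an extended liver work-up. If sites resolve the wording differently, patients with identical values will be stopped and reported at one site and not at another. The table also disagrees with itself on whether the deciding measurement is taken at all.

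**Working it through.** No sample size or error rate is involved, so the check is a truth table. Let A = ALT ≥3×ULN, B = total bilirubin ≥2×ULN and C = direct fraction >35%. A value of 1 means that the condition, or the criterion, is met.

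The text admits four forms:

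- **F1:** A and (B or C). This is the natural reading of criterion 1 and of Section 3.2.1.
- **F2:** (A and B) or C. The missing brackets also allow this.
- **F3:** A and B and C. This is footnote 2 with the parenthesis as a requirement.
- **F4:** A and B. This is footnote 2 with the parenthesis as a descriptive gloss.

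| A | B | C | F1 | F2 | F3 | F4 |
|---|---|---|---|---|---|---|
| 0 | 0 | 0 | 0 | 0 | 0 | 0 |
| 0 | 0 | 1 | 0 | 1 | 0 | 0 |
| 0 | 1 | 0 | 0 | 0 | 0 | 0 |
| 0 | 1 | 1 | 0 | 1 | 0 | 0 |
| 1 | 0 | 0 | 0 | 0 | 0 | 0 |
| 1 | 0 | 1 | 1 | 1 | 0 | 0 |
| 1 | 1 | 0 | 1 | 1 | 0 | 1 |
| 1 | 1 | 1 | 1 | 1 | 1 | 1 |

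F1 and F3 differ in two of the eight combinations; F1 and F4 differ in one. F2 would stop a patient on the direct fraction alone, whatever the ALT. That is unlikely to be meant, but only brackets exclude it.

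**First area of disagreement (A = 1, B = 0, C = 1).** Example: ALT 3.5×ULN, total bilirubin 0.8×ULN, direct fraction 40%, no symptoms, monitored weekly. F1 says stop and report. Under F3 or F4 criterion 1 is not met, and the values fit the first row.

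**Second area (A = 1, B = 1, C = 0).** Example: ALT 4×ULN, total bilirubin 2.5×ULN, direct fraction 20%. F1 and F4 say stop; F3 does not. The first row would not cover this patient either, because total bilirubin is not below 2×ULN.

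**Which lines support which form.** The work-up instruction (fractionate at total bilirubin ≥2×ULN) and the description of criteria 1–2 patients as having abnormal total bilirubin fit the footnote form. Footnote 1, with no threshold, fits F1. Scheduled chemistry in Section 4.1, note B, lists total bilirubin only. A patient in the first area is therefore recognised only if someone fractionates a bilirubin below 2×ULN, which footnote 1 asks for and the work-up line does not.

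**Reach.** Criterion 3 stops treatment at ALT ≥5×ULN. Criteria 2 and 4–6 stop it for raised INR, ALT ≥3×ULN persisting for at least 4 weeks, inability to monitor weekly, or liver or hypersensitivity symptoms, subject to their stated exemptions. The decision to stop thus turns on the reading only for the remainder, chiefly ALT 3 to below 5×ULN without symptoms and with weekly monitoring.

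Reporting and work-up are affected more widely. With ALT 6×ULN, total bilirubin 0.8×ULN and direct fraction 40%, criterion 3 stops treatment under every form. The criteria 1–2 SAE report, the repeat within 24 hours (rather than 24–72 hours) and the additional work-up still depend on whether criterion 1 is also met.

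**The case against.** The strongest reply is that the two operative lines, criterion 1 and the Section 3.2.1 trigger, agree word for word on the connector. Footnote 2 is not itself a stopping line: it says which events may indicate severe injury, and a footnote can single out a graver subset of a broader rule. The work-up line applies after a patient has stopped and does not define who stops. Each of these observations is correct. They do not settle the matter, because the footnote is attached to the criterion it restates, the criteria 1–2 headings presuppose abnormal total bilirubin, and the criterion has no brackets.

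Four stronger inferences are tempting and should not be drawn:

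- **That the first row separately contradicts criterion 1.** It expressly yields to the stopping list ("If liver chemistry stopping criteria are met any time, proceed as described below"), so the doubt comes from criterion 1 and its footnotes alone.
- **That Hy's Law counts would differ.** Hy's Law is named only in footnote 2, and this protocol defines no such count or endpoint.
- **That patients with liver metastases would be stopped on the first day of treatment.** The baseline exemption for ALT 3–5× is indeed written only into criteria 4 and 5, but that may be deliberate. The scenario also needs a baseline direct fraction that the schedule does not require, and the remaining eligibility limits sit in the Master Protocol, which is not shown.
- **That about 3% of the cohort is at stake.** 1/35 = 2.9% is the weight of any single patient against the accrual goal of 35. It says nothing about how often the conflict arises.

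**Conclusion.** The inconsistency is real and confined to wording. Criterion 1 and the Section 3.2.1 trigger state one relation, footnote 2 states another, and the supporting lines divide between them. The forms disagree for ALT ≥3×ULN with total bilirubin <2×ULN and direct fraction >35%. If the parenthesis in footnote 2 is a requirement, they also disagree for ALT ≥3×ULN with total bilirubin ≥2×ULN and direct fraction ≤35%.

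The effect on discontinuation is limited to patients whom criteria 2–6 do not stop; the effect on SAE reporting and work-up is broader. The documents give no frequency for either group, and no effect on a trial result has been shown. The case for correcting it is that this is a mandatory safety rule which should give the same action for the same values at every site. The conclusion takes footnote 2 as explaining criterion 1, as its superscript indicates. It takes no position on which relation is clinically right.

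**What to change.** Reconcile five places so that they state one explicit, bracketed relation between ALT, total bilirubin and direct fraction: criterion 1, footnote 1, footnote 2 and the fractionation instruction in Table 7, and the liver trigger in Section 3.2.1. State also when the fraction is to be measured, since the work-up line and footnote 1 now differ. The description of criteria 1–2 patients as having abnormal total bilirubin should be checked against the chosen wording. The choice of relation belongs to the sponsor and the drug-safety team.

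The cost is a wording change in Table 7 and Section 3.2.1 at the next addendum, with no added patients or visits. If the chosen relation needs the fraction at total bilirubin below 2×ULN, the work-up instruction must ask for it there; footnote 1 already does so where testing is available.

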3.5.2 Guidelines for Prolonged QTc

Guidelines for dose modification and stopping criteria due to QTc-prolongation are provided (see Table 8).

Table 8 Withholding and Stopping Criteria for QTc-Prolongation

QTc-Prolongation ^a	Action and Dose Modification

 • QTcB \geq 501 msec, or • Uncorrected QT > 600 msec, or • QTcB > 530 msec for subjects with bundle branch block 	
 • Interrupt all study treatments until QTcB prolongation resolves to grade 1 or baseline • Test serum potassium, calcium, phosphorus and magnesium. If abnormal correct per routine clinical practice to within normal limits. • Review concomitant medication usage for a prolonged QTc. • Restart at current dose level^b • If event does not resolve or recurs after restarting, permanently discontinue study treatments.

Abbreviations: msec = milliseconds; QTcB = QT interval on electrocardiogram corrected using the Bazett's formula

A: Based on average QTc value of triplicate ECGs. For example, if an ECG demonstrates a prolonged QT interval, obtain two or more ECGs over a brief period, and then use the averaged QTc values of the three ECGs to determine if study treatments should be interrupted or discontinued.

B: If the QTc prolongation resolves to grade 1 or baseline, the subject may resume study treatment if the investigator and the subprotocol Study Chair agree that the subject will benefit from further treatment.

Rev. 8/15

Rev. 8/15

3.5.3 Guidelines for Rash

Rash is a frequent AE observed in subjects receiving trametinib (see the Investigator’s Brochures [4]) for more information). Recommendations for supportive care and guidelines for dose modifications for rash are based on experience with other MEK inhibitors and EGFR inhibitors [26, 27] and are provided (see Table 9 and Table 10).

The institutional standards for the management of skin-related AEs can differ from these guidelines. In this case, best clinical judgment should be applied and a consultation with the the subprotocol Study Chair may be required.

Table 9 Guidelines for Supportive Care of Rash

Type of Care	Action
Prevention/Prophylaxis ^a	
 • Avoid unnecessary exposure to sunlight • Apply broad-spectrum sunscreen (containing titanium dioxide or zinc oxide) with a skin protection factor (SPF) ≥ 15 at least twice daily. • Use thick, alcohol-free emollient cream (e.g., glycerine and cetomacrogol cream) on dry areas of the body at least twice daily. • Topical steroids and antibiotics should be applied at least twice daily starting on Day 1 of study treatment, to body areas such as face, chest, and upper back. 
Use mild-strength topical steroid (hydrocortisone 1% cream) or or topical antibiotic (e.g., clindamycin) or oral antibiotics (e.g., doxycycline 100 mg BID, minocycline 100 mg BID)

Symptomatic Care ^b	
 • Pruritic lesions: cool compresses and oral antihistamine therapies • Fissuring lesions: Monsel’s solution, silver nitrate, or zinc oxide cream • Desquamation: thick emollients and mild soap • Paronychia: antiseptic bath, local potent corticosteroids in addition to oral antibiotics; if no improvement, consult dermatologist or surgeon • Infected lesions: appropriate bacterial/fungal culture-driven systemic or topical antibiotics

Abbreviations: BID = twice daily; SPF = sun protection factor

- a. Rash prophylaxis is recommended for the first 6 weeks of study treatment
- b. Subjects who develop rash/skin toxicities should be seen by a qualified physician and should receive evaluation for symptomatic/supportive care management

Guidelines for management and dose reduction for rash considered to be related to study treatment are provided (see Table 10).

Table 10 Management and Dose Modification Guidelines for Rash

CTCAE Grade	Adverse Event Management	Action and Dose Modification
Grade 1	
 Initiate prophylactic and symptomatic treatment measures^a Use moderate strength topical steroid^b Reassess after 2 weeks 	
 Continue study treatment If rash does not recover to baseline within 2 weeks despite best supportive care, reduce trametinib by one dose level^c
Grade 2	
 Initiate prophylactic and symptomatic treatment measures Use moderate strength topical steroid^b Reassess after 2 weeks 	
 Reduce trametinib by one dose level 
 If rash recovers to \leq grade 1 within 2 weeks, increase dose to previous dose level If no recovery to \leq grade 1 within 2 weeks, interrupt study treatment until recovery to \leq grade 1 Restart trametinib at reduced dose level^c
Grade \geq 3	
 Use moderate strength topical steroids^b PLUS oral methyl-prednisolone dose pack Consult dermatologist 	
 Interrupt trametinib until rash recovers to grade \leq 1 Restart^c trametinib reduced by one dose level^d If no recovery to grade \leq 2 within 2 weeks, permanently discontinue trametinib

Abbreviations: CTCAE = Common Terminology Criteria for Adverse Events

- a. Rash prophylaxis is recommended for the first 6 weeks of study treatment
- Rev. 2/16 b. Moderate-strength topical steroids: hydrocortisone 2.5% cream or fluticasone propionate concentration 0.05% cream
- Rev. 8/15 c. Approval of the subprotocol Study Chair is required to restart study treatment after > 2 weeks of interruption.
- d. Escalation of study treatment to previous dose level may be considered if no rash is evident 4 weeks after restarting study treatment

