3.4 Dose Modifications

NOTE: Patients who interrupt trametinib for > 2 weeks will be removed from this subprotocol, unless the interruption was for reduction in LVEF, visual changes or RPED with subsequent recovery as described in corresponding tables below.

All toxicity grades below are described using the NCI Common Terminology Criteria for Adverse Events (CTCAE) version 4.0.

All appropriate treatment areas should have access to a copy of the CTCAE version 4.0. A copy of the CTCAE version 4.0 can be downloaded from the CTEP website (<http://ctep.cancer.gov>).

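### A Grade ≥3 rash that has improved only to Grade 2 after two weeks of hold stays on hold under Table 10 but is removed under the Section 3.4 note

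*Protocol*

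**What the plan says.** Three statements in the protocol govern a trametinib hold for rash.

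- **Table 10, Grade ≥3 row (Section 3.5.3).** The hold is worded "Interrupt trametinib until rash recovers to grade" ≤ 1, after which the drug restarts one dose level lower. The stop rule uses a different grade: no recovery to grade ≤ "2 within 2 weeks, permanently discontinue trametinib".
- **Table 10, footnote c.** It is attached to the restart instruction in both the Grade 2 row and the Grade ≥3 row: "Approval of the subprotocol Study Chair is required to restart study treatment after > 2 weeks of interruption".
- **The note at the start of Section 3.4.** "Patients who interrupt trametinib for > 2 weeks will be removed from this subprotocol, unless the interruption was for reduction in LVEF, visual changes". The one remaining exception is RPED, and recovery has to follow. Rash is not listed.

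For comparison, the Grade 2 and Grade 3 rows of Table 6 (pneumonitis, Section 3.4.5) restart at Grade ≤1 and stop if there is no recovery to grade ≤ "1 within 2 weeks, permanently discontinue trametinib". There the restart and stop grades are the same, and the row agrees with the Section 3.4 note.

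**The concern.** Restart and stop use different grades in the Grade ≥3 rash row. Between them lies a patient whose rash has improved from Grade 3 or worse to Grade 2 but no further. Table 10 treats this patient as still on hold and still able to return to treatment. Section 3.4 treats the same patient, once past two weeks, as off the subprotocol. A site can follow either text and believe that it complies.

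The choice affects the patient's exposure to trametinib, the time spent on the arm, and whether the patient counts as a removal for toxicity. The schema gives an accrual goal of 35, so each patient handled differently moves a proportion by 1/35 = 2.9 percentage points.

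**Working it through.** No sample-size or error-rate figure is involved. The check is to apply each rule to every rash grade possible at the end of two weeks of hold.

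**Step 1. A rash that began at Grade ≥3.**

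| Rash at 2 weeks of hold | Table 10, Grade ≥3 row with footnote c | Section 3.4 note, once the hold exceeds 2 weeks | Same result? |
|---|---|---|---|
| Grade ≤1 | Restart, one dose level lower | Not reached if the restart is prompt | Yes |
| Grade 2 | Stop rule not met; hold continues to Grade ≤1; later restart possible with Study Chair approval | Removed from the subprotocol | **No** |
| Grade ≥3 | Permanent discontinuation | Removed from the subprotocol | Yes, in effect |

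**Step 2. What is left of Table 10 if the note governs.** A patient at Grade ≥3 is stopped at two weeks by the row. A patient at Grade 2 is removed as soon as the hold passes two weeks. The two patients are separated only at the boundary itself, so the Grade ≤2 limit has almost no effect. Footnote c speaks only to restarts after more than two weeks, by which time the note has already removed the patient, so it too has almost no case to act on.

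**Step 3. What is left of the note if Table 10 governs.** The note's exceptions would then have to include rash, and they do not.

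**Step 4. The Grade 2 row of Table 10.** That row first lowers the dose. If the rash has not reached Grade ≤1 within two weeks, it interrupts treatment until it does. It has no stop rule and no time limit, and its restart carries footnote c. A hold in this row that runs past two weeks meets the same conflict: restart with approval under footnote c, removal under the note.

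**Step 5. Other text that might settle it.** Table 12 discontinues after a delay of 14 days or more, but states that it does not cover rash. Section 3.5.3 allows clinical judgment where institutional standards differ from its guidelines, which does not rank one protocol statement over another.

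**Step 6. Size.** Section 1.1.3 reports Grade 3 or 4 rash in less than 8% of 211 patients in the phase III melanoma study. Assuming that rate carries over to this arm, the expected number entering the Grade ≥3 row is below 35 × 0.08 = 2.8. The share of these at Grade 2 after two weeks is not given. The 57% in Section 1.1.3 is rash of any grade and does not give the number entering either row.

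**The case against.** The best defence is that the looser stop grade is deliberate. Read alone, the row gives three outcomes at two weeks: restart at Grade ≤1, keep holding an improving rash at Grade 2, stop at Grade ≥3. Footnote c fits this reading, because if the stop grade were also ≤1, hardly anyone in this row could still be waiting to restart after two weeks. This stands: the difference between the two grades is not in itself an error. But it sharpens the conflict with Section 3.4, since the outcome it preserves for Grade 2 is the one that the note removes.

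One could also read footnote c as a specific exception to a general rule. The note, however, lists its own exceptions ("will be removed from this subprotocol, unless the interruption was for reduction in LVEF, visual changes or RPED") and refers to their tables. Rash is not there, and footnote c does not mention the note.

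Section 3.5.3 is also guidance, under which "In this case, best clinical judgment should be applied". This softens the practical harm. It applies where institutional standards differ, and does not say whether a patient past two weeks remains on the subprotocol.

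A reader might go further and infer that a Grade 2 rash leaves the patient on hold without end. The documents do not support that: the note limits a rash hold to two weeks. Nor is a row without its own time limit peculiar to this case. The Grade 2 row of Table 10 and the Grade 3 or 4 (or complicated) diarrhea row of Table 11 also hold to Grade ≤1 with no row-level limit, and Section 3.4 can serve as the general cap.

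**Conclusion.** The point holds as a contradiction between two sections. For a Grade ≥3 rash that is at Grade 2 after two weeks of hold, Table 10 with footnote c keeps the patient and allows a later restart, while the Section 3.4 note removes the patient. The same conflict over footnote c reaches holds under the Grade 2 row. The conclusion rests only on the wording of these passages and on rash being absent from the note's exceptions.

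The number of patients affected cannot be derived from the documents. A reader might take as its measure the chance that at least one of 35 patients enters the Grade ≥3 row: 1 − 0.95^35 = 83% to 1 − 0.921^35 = 94%, for rates of 5% to 7.9%. That is the chance of entering the row, not of being at Grade 2 two weeks later, and the 5% is an assumption, since the protocol says only less than 8%. The affected group is likely to be small, but the arm is small too. The inconsistency merits correction and does not undermine the design.

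**What to change.** Reconcile the Section 3.4 note with Table 10 so that each rash grade at two weeks of hold leads to one stated outcome. Three items must agree with the note: the restart and stop thresholds in the Grade ≥3 row, footnote c in that row, and footnote c in the Grade 2 row. Aligning the two grades in the Grade ≥3 row alone would leave the Grade 2 row in conflict. Which outcome applies is a clinical choice for the sponsor.

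The cost is a short text change at the next amendment, with no added visits, assessments or patients.
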